5.3 Variables

5.3.1 Exposure definition and measures

Exposure information recorded will include start and stop dates, dose, dosing frequency, and reason for discontinuation (if applicable).

The following criteria will be used to assign women to one of the cohorts:

- Cohort A: Exposure to QUVIVIQ at any point during the patient's pregnancy or at any time within 5 half-lives prior to conception.
- Cohort B:
 - Cohort B1: No exposure to QUVIVIQ or any other ORA (including, suvorexant, lemborexant, any ORA newly approved during the study period, or any ORA in pre-marketing clinical studies) but exposure to another insomnia medication [Appendix 3] during pregnancy or within 5 half-lives of the respective medication prior to conception.
 - Cohort B2: No exposure to any insomnia medication during pregnancy and within
 5 half-lives of the insomnia medication taken prior to conception.

Women with retrospective pregnancies will be considered to have been exposed to QUVIVIQ if there is documentation of exposure to QUVIVIQ at any point during the patient's pregnancy or at any time within 5 half-lives prior to conception.

Exposure assessments will not be determined for the external comparator cohort(s), as patient-level data is not available; these cohorts represent the prevalence of birth defects in the general population.

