5.7.2 Planned method of analysis

5.7.2.1 General considerations

Descriptive analyses will be performed to gain an understanding of the qualitative and quantitative nature of the data collected and the characteristics of the sample studied. Continuous variables will be reported as mean (and standard deviation), median, minimum, maximum, and range where appropriate. Categorical variables will be summarized as number and proportion of the total study population, and by subgroups where appropriate.

Data analysis for major congenital malformations will be based on exposure to QUVIVIQ or treatments for insomnia within 5 half-lives prior to conception or the first trimester. The primary analysis set will exclude women who have received first trimester prenatal screening in which either aneuploid disorders or genetic disorders causing major congenital malformations have been detected, because these disorders are unrelated to medication use. Prematurity-related disorders and transient conditions will also be excluded from the analysis of major congenital malformations.

Confidential

Analyses for the secondary outcomes will be conducted overall (encompassing preconception [within 5 half-lives prior to conception] and the entire pregnancy) as well as separately for preconception and each trimester (first trimester: conception to 13^{+6} weeks' gestation; second trimester: 14^{+0} to 27^{+6} weeks' gestation; third trimester: $\geq 28^{+0}$ weeks' gestation) as sample size allows. See Appendix 4 for the outcome-specific exposure-windows that will be evaluated. Gestational age will be determined based on results from the first available ultrasound or the date of the LMP when an ultrasound is not available [ACOG 2017, EMA 2005].

If sufficient numbers are obtained, analyses will also be presented by the subgroups of maternal age, race/ethnicity, prior history of elective or therapeutic pregnancy termination status, prenatal screening result (positive vs negative), prenatal testing status (performed vs not performed), and other important risk factors [see Section 5.7.4.4].

Any patient who is enrolled in the Cohort A or Cohort B and then becomes exposed to any ORA during pregnancy will be addressed in the analysis depending on the medication, the timing of the exposure, and the outcome of interest.

All computations and generations of tables, listings, and data for figures will be performed using SAS® version 9.4 or higher.

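### Read literally, the cohorts are defined by exposure to the end of pregnancy, so Cohort B2 keeps early losses and loses longer pregnancies, and the A vs B2 risk ratios for spontaneous abortion and termination fall below 1 with no drug effect

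*Protocol*

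**What the plan says.** All places are in the protocol.

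- **Cohorts (5.3.1).** A is "Exposure to QUVIVIQ at any point during the patient's pregnancy or at any time within 5 half-lives prior to conception". B1 is no ORA "but exposure to another insomnia medication" in pregnancy or the preconception window. B2 is "No exposure to any insomnia medication during pregnancy and within" 5 half-lives of any such drug taken before conception. None of the three definitions has a cut-off at enrollment or at any gestational age.
- **Exposure window (5.7.2.1).** For secondary outcomes: "Analyses for the secondary outcomes will be conducted overall (encompassing preconception [within 5 half-lives prior to conception] and the entire pregnancy", with separate trimester analyses where numbers allow. For malformations: "Data analysis for major congenital malformations will be based on exposure to QUVIVIQ or treatments for insomnia within" 5 half-lives of conception or in the first trimester.
- **Exposure starting later (5.7.2.1).** The one rule covers a patient "enrolled in the Cohort A or Cohort B and then becomes exposed to any ORA during pregnancy". Nothing addresses a B2 woman who starts a non-ORA drug.
- **Updating (5.6.1.2).** Insomnia treatment is re-collected at about 14, 21 and 34 weeks and at delivery, so later use will be seen.
- **Estimators (5.7.4.2, 5.7.4.3).** Spontaneous abortion is a crude proportion of all pregnant women, termination is handled in the same way, and A is compared with B2 by risk ratio.

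**The concern.** Under these definitions, B2 membership depends on drug use that has not yet happened when a woman enrolls. Take an unexposed woman whose pregnancy ends at 10 weeks: she has had almost no time to take a listed drug and stays in B2. A similar woman who carries to term has most of a pregnancy in which to take one. Appendix 3 includes over-the-counter melatonin, diphenhydramine and doxylamine. Once she takes any of these she no longer meets the B2 definition and does meet the B1 definition.

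B2 is therefore enriched for short pregnancies. A crude proportion does not correct for this, because it takes no account of time at risk. At stake is a stated secondary objective, the comparison of A with B2, for the two outcomes that most shorten a pregnancy. A risk ratio below 1 could be read as reassurance when it comes only from how B2 is defined.

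**Working it through.** **The plan's own figure.** Table 4 gives power above 99.9% for spontaneous abortion, A vs B2, at a risk ratio of 2.5. The inputs are 204 and 194 women, 11.55% and 11.0%, and a margin of 16.5%.

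SE = √(0.1155×0.8845/204 + 0.11×0.89/194) = 0.0317. Power = Φ((0.165 − 0.0055)/0.0317 − 1.96) = 99.89%, which agrees after rounding. The stillbirth row (39.8, 62.9 and 82.0%) reproduces exactly. These calculations take the same true background rate in every comparator and allow nothing for movement between cohorts.

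**Model 1: first use spread evenly over weeks 6 to 39.**

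Inputs per 100 initially unexposed women, rates from Table 4:
- spontaneous abortion 11 and termination 18 (both assumed at week 10)
- stillbirth 1.4 (assumed week 30)
- remaining births 69.6, of which 11% are preterm: 7.7 (assumed week 34) and 61.9 at term (assumed week 39)

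The assumed proportion starting a drug by term is q. The share still in B2 at week w is 1 − q(w − 6)/33.

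Worked for q = 20%:
- week 10: 1 − 0.20×4/33 = 0.976, leaving 10.73 abortions and 17.56 terminations
- week 30: 0.855, leaving 1.20
- week 34: 0.830, leaving 6.39
- week 39: 0.800, leaving 49.52
- total left in B2: 85.41

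B2 spontaneous abortion = 10.73/85.41 = 12.6%. The null A/B2 risk ratio = 11.0/12.57 = 0.88. Termination = 17.56/85.41 = 20.6%, with the same ratio because the assumed timing is the same.

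The last column applies Appendix 4, which lists no third-trimester window for spontaneous abortion. Starts after week 28 then remove nobody, so exits stop at q×22/33.

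| q (assumed) | B2 spontaneous abortion | B2 termination | Null A/B2 ratio, both | Spontaneous abortion ratio, window to week 28 |
|---|---|---|---|---|
| 5% | 11.3% | 18.6% | 0.97 | 0.98 |
| 10% | 11.7% | 19.2% | 0.94 | 0.96 |
| 20% | 12.6% | 20.6% | 0.88 | 0.92 |
| 30% | 13.6% | 22.2% | 0.81 | 0.88 |
| 40% | 14.8% | 24.2% | 0.74 | 0.84 |

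**Model 2: constant hazard from enrollment at week 10.** Abortions are spread to week 20, terminations to week 24 and stillbirths over weeks 20 to 40; live births are at week 39.

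For 20% starting by week 40, the hazard is −ln(0.8)/30 = 0.00744 per week. Shares retained are 0.964 (abortion), 0.950 (termination), 0.863 (stillbirth) and 0.806 (live birth). Overall retention = 0.11×0.964 + 0.18×0.950 + 0.014×0.863 + 0.696×0.806 = 0.850. The null ratio is 0.850/0.964 = 0.88 for abortion and 0.850/0.950 = 0.90 for termination (0.895 unrounded).

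At 5, 10, 20 and 40% the ratios are:
- spontaneous abortion: 0.97, 0.94, 0.88, 0.76
- termination: 0.97, 0.95, 0.90, 0.78
- stillbirth: between 1.00 and 0.97

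Assuming enrollment at week 6 or 14 gives nearly the same figures.

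**Other comparisons, Model 2 at 20%.** Women leaving B2: 194×0.150 = 29.1, carrying 194×0.11×0.036 = 0.77 abortions. If all join B1, its proportion is (387×0.11 + 0.77)/(387 + 29.1) = 10.4%, and the A/B1 ratio is 1.06. Over 5 to 40% this ratio runs from 1.01 to 1.11. Overall B still holds 581×0.11 = 63.9 abortions in 581 women, so A vs B is unchanged by moves from B2 to B1.

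**With the fix.** If status is fixed at enrollment, the null A/B2 ratio in this model is 1.00.

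**The case against.** The strongest reply is that cohort is set at enrollment. B2 status is an eligibility criterion (5.2.1.1), targets count women enrolled per cohort (5.5.1, 5.9.3), and the ORA rule speaks of women already enrolled in a cohort who become exposed afterwards. No sentence says that a later non-ORA starter is moved to B1. On that reading there is no bias. This reading is possible, but it is stated nowhere. It also sits badly with 5.3.1, whose B2 wording covers the whole pregnancy, and with the exposure window in 5.7.2.1. The SAP could add a method, but the definition is fixed in the protocol.

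Trimester analyses do not settle it: they depend on sample size and do not redefine B2. The Table 6 analysis by gestational age at enrollment is limited to women in the primary analysis, which is A vs B1.

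Four limits stand in full. The uptake rate is assumed. Appendix 4 may shorten the window for spontaneous abortion. Stillbirth hardly moves. Censoring B2 alone would leave the same flaw in A and B1, which are ever-exposed.

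A reader might also infer that a woman first treated at 30 weeks is lost to every malformation comparison, shrinking the B2 controls. The protocol does not support that. The first-trimester window in 5.7.2.1 arguably keeps her as unexposed, and she remains in overall Cohort B in any case. What stands is that 5.3.1 and 5.7.2.1 do not say the same thing about her.

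**Conclusion.** The point holds for A vs B2 on spontaneous abortion and termination, if the definitions are applied as written. With no drug effect the ratio falls to about 0.97 to 0.74 for an assumed 5 to 40% uptake by term; two different timing models agree closely. For spontaneous abortion, model 1 gives 0.98 to 0.84 if the window ends with the second trimester. The direction follows from the definitions; the size rests on an uptake rate and on timings that the protocol does not give.

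A reader might infer that the definition favours QUVIVIQ throughout. It does not: A vs B1 shifts against QUVIVIQ, moves from B2 to B1 cancel in A vs overall B, and the primary malformation analysis does not use B2. The likely harm is to the A vs B2 point estimates more than to the margin test: even at 40% in model 1 the shift in the spontaneous abortion difference is 11.0 − 14.8 = −3.8 percentage points, against a margin of 16.5 at a risk ratio of 2.5.

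**What to change.** Change 5.3.1 and 5.7.2.1 as follows.

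1. For spontaneous abortion, termination and other outcomes that depend on the length of pregnancy, classify every woman in A, B1 and B2 by exposure up to enrollment. Alternatively, treat exposure as time-varying with entry at enrollment. Either way, say that insomnia drug use starting later never reclassifies earlier pregnancy time. The rule must cover all three cohorts and all listed drugs, not ORAs alone.
2. For malformation comparisons, state that B2 membership uses the same window as exposure: from 5 half-lives before conception to the end of the first trimester. Later use then does not remove a B2 control, and 5.3.1 agrees with 5.7.2.1.

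The cost is wording and a derived exposure flag, since start and stop dates are already collected. With time-varying exposure, some estimates become time-to-event rather than crude proportions. With enrollment status, a few late starters are analysed as unexposed although they later took a drug.

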5.7.4.2 Analysis of primary and secondary endpoints

The prevalence of major and minor congenital malformations will be calculated using the MACDP convention. If needed for future analyses, minor and major congenital malformations will also be calculated using the EUROCAT convention using the same process. Major malformations will be analyzed separately from minor malformations, with the primary analysis including only adjudicated major congenital malformations. The total prevalence will be calculated by dividing the number of women with any adjudicated cases of each event (observed in live births, fetal deaths, elective or therapeutic terminations, and at any gestational age) by the total number of pregnancies (excluding spontaneous terminations and ectopic or molar pregnancies). The prevalence at birth will be calculated as number of cases observed in live births and stillbirths divided by the total number of births (stillbirths + live births). Data analysis for major congenital malformations will be based on exposure to QUVIVIQ from within 5 half-lives prior to conception through the end of the first trimester.

Confidential

The prevalence of pregnancy complications, including preeclampsia, pregnancy-induced hypertension, gestational diabetes, and preterm labor, will be summarized by dividing the number of pregnant women with that complication by the total number of pregnant women.

The prevalence of spontaneous abortions will be calculated by dividing the number of women with fetal loss occurring before 20 weeks gestation by the total number of pregnant women.

The prevalence of elective and therapeutic abortion will be estimated similarly as separate outcomes.

The prevalence of preterm birth will be calculated by dividing the number of cases by the total number of births (stillbirths + live births). The prevalence of small for gestational age will be calculated by dividing the number of cases by the total number of live births.

For other events of interest occurring in developing neonates and infants, including mortality, hospitalizations for serious illness, growth, and developmental delays, the prevalence will be calculated as the number of cases divided by the total number of live births.

The prevalence of primary and secondary outcome measures will be presented with 97.5% CIs for binomial proportion. The analyses summarized in this section will be performed on the Cohort A and Cohort B.

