5.7.4.3 Comparative analyses

Internal comparator analysis

Only prospective pregnancies will be included in the internal comparator analysis. As described in Section 5.7.1.3 in the primary analysis of major congenital malformations, Cohort A will be compared to Cohort B1. In a secondary analysis of major congenital malformations, Cohort A will be compared to Cohort B overall and Cohort B2. All secondary outcome proportions in Cohort A will be compared to Cohort B, as well as separately with Cohorts B1 and B2 using the risk ratio (one-sided 97.5% CIs). The difference in proportions will also be compared to the defined clinical equivalence margin to reject the hypothesis that the rate in Cohort A is higher than in Cohort B1. Also, comparisons may be explored using risk ratios adjusted to relevant covariates through methods such as propensity score weighting, if the sample size is sufficient in subgroups of the covariates. The key covariates of interest that will be considered for adjustment are maternal age, prior history of elective or therapeutic pregnancy termination status, other

Confidential

insomnia treatment exposures, and baseline alcohol, smoking, marijuana, and drug use. Other prior pregnancy and prior infant outcomes will be explored and considered for adjustment at the time of analysis.

The primary and secondary outcomes will be evaluated and described among subgroups of patients defined by key characteristics of interest including maternal age, race/ethnicity, smoking, and exposure to other insomnia medications [see Section 5.7.4.4].

External comparator cohort analysis

Prevalence for major congenital malformations in Cohort A will be assessed in parallel to the prevalence observed in available external comparator cohort(s) representing the background prevalence of birth defects in the general US and EEA population. The MACDP and EUROCAT classification of congenital malformations will be implemented to ensure comparability to US and EEA populations, respectively.

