Appendix 4 List of exposure windows for secondary outcomes

As detailed in the FDA's *Postapproval Pregnancy Safety Studies, Guidance for Industry Section B.10* [FDA 2019a], separate analyses will be performed for each pregnancy outcome. The primary analysis for major congenital malformations will be based on exposure to QUVIVIQ within 5 half-lives prior to conception or the first trimester [see Sections 5.7.1.3 and 5.7.4.4]. For the secondary outcomes, subgroup analyses based on the timing of exposure (preconception, first trimester, second trimester, third trimester) will be conducted as sample size permits. Consistent with prior research on sleep medications in pregnancy [Huitfeldt 2020, Lupattelli 2019, Calderon-Margalit 2009, Wang 2010], each outcome will be assessed with respect to exposure timing as outlined in this table.

Secondary outcome of interest	Exposure timing for evaluation in analyses	
Pregnancy complications		
Preeclampsia	Preconception, first trimester, second trimester, third trimester	
Pregnancy-induced hypertension	Preconception, first trimester, second trimester, third trimester	
Preterm labor	Preconception, first trimester, second trimester, third trimester	
Gestational diabetes	Preconception, first trimester, second trimester, third trimester	
Pregnancy outcomes		
Elective and therapeutic abortion	Preconception, first trimester, second trimester, third trimester	
Spontaneous abortion	Preconception, first trimester, second trimester	
Fetal death or stillbirth	Preconception, first trimester, second trimester, third trimester	
Live birth	Preconception, first trimester, second trimester, third trimester	
Preterm birth	Preconception, first trimester, second trimester, third trimester	

Confidential

Infant outcomes		
Minor congenital	Preconception, first trimester, second trimester, third	
malformations	trimester	
Size for gestational age	Preconception, first trimester, second trimester, third trimester	
Infant death	Preconception, first trimester, second trimester, third trimester	
Hospitalization for serious	Preconception, first trimester, second trimester, third	
illness	trimester	
Postnatal growth and	Preconception, first trimester, second trimester, third	
development	trimester	

Preconception: within 5 half-lives prior to conception (LMP + 14 days), First trimester: conception to 13⁺⁶ weeks' gestation, Second trimester: 14⁺⁰ to 27⁺⁶ weeks' gestation, Third trimester: 28⁺⁰ weeks' gestation to end of pregnancy.

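### Second- and third-trimester exposure analyses of losses, terminations and pregnancy complications do not align the Cohort B2 and B risk sets with the exposed women

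*Protocol*

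**What the plan says.** - **Strata.** Protocol section 5.7.2.1 analyses secondary outcomes overall "as well as separately for preconception and each trimester", with the second trimester starting at 14+0 weeks and the third at 28+0. Appendix 4 forms the strata by exposure: "subgroup analyses based on the timing of exposure (preconception, first trimester, second trimester, third trimester) will be conducted as sample size permits". All three trimesters are listed for every outcome except spontaneous abortion, which stops at the second.
- **Comparators.** Section 5.7.4.3: "All secondary outcome proportions in Cohort A will be compared to Cohort B, as well as separately with Cohorts B1 and B2".
- **Unexposed group.** Section 5.3.1: "Cohort B2: No exposure to any insomnia medication during pregnancy and within" five half-lives before conception. A B2 woman therefore has no exposure trimester.
- **Denominators (section 5.7.4.2).** Spontaneous abortion is women with "fetal loss occurring before 20 weeks gestation by the total number of pregnant women". For terminations, "The prevalence of elective and therapeutic abortion will be estimated similarly as separate outcomes". Complications are the "number of pregnant women with that complication by the total number of pregnant women". By contrast, "The prevalence of preterm birth will be calculated by dividing the number of cases by the total number of births (stillbirths + live births"), and small for gestational age and the infant outcomes are divided by live births. No denominator is given for live birth or stillbirth.

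**The concern.** Each rule is reasonable alone; the difficulty is in the combination. Belonging to the second- or third-trimester QUVIVIQ stratum requires a pregnancy that has lasted to that trimester. Nothing requires this of B2, or of the B2 part of B. Applied as written, the rules set women who reached 14+0 or 28+0 weeks against a group that includes pregnancies already ended by then. This is survivor (immortal-time) selection, and it remains even when every exposure precedes its outcome.

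In a safety registry the main risk is false reassurance: a real excess of second-trimester losses or terminations could be reported as no difference or as a reduction. For complications that arise late, the same mismatch can produce a false signal of harm.

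**Working it through.** **The plan's own figures.** The protocol gives no figure for a trimester-specific comparison. Table 4 does show what base it uses for these outcomes. Power = Φ[(margin − (P_A − P_B))/SE − 1.96], with SE² = P_A(1−P_A)/n_A + P_B(1−P_B)/n_B. For preeclampsia (4.83% vs 4.6%, margin 6.9 points) and n = 204 in A against 387, 194 and 581, this gives 95.2%, 88.1% and 97.0%; Table 4 states 95.5%, 88.4% and 97.4%. So power for these outcomes rests on all enrolled women, as Table 4 footnote a says.

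**Inputs.** From Table 4: spontaneous abortion 11%, termination 18%, live birth 62%, stillbirth 1.4%. The protocol does not say how these are distributed over gestation, so the following are assumptions: f = share of spontaneous abortions before 14+0, g = share of terminations before 14+0, L = share of all pregnancies ended before 28+0.

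**Spontaneous abortion, second-trimester exposure vs all B2, no drug effect.** Share still ongoing at 14+0: S = 1 − 0.11f − 0.18g. Null RR = (1 − f)/S.

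| f | g | S | Null RR | True RR that would show as 1.0 |
|---|---|---|---|---|
| 0.3 | 0.9 | 0.805 | 0.87 | 1.15 |
| 0.3 | 0.5 | 0.877 | 0.80 | 1.25 |
| 0.5 | 0.5 | 0.855 | 0.58 | 1.71 |
| 0.8 | 0.5 | 0.822 | 0.24 | 4.11 |
| 0.9 | 0 | 0.901 | 0.11 | 9.01 |

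**Terminations, second-trimester exposure.** Null RR = (1 − g)/S.
- Half before 14+0 (g = 0.5): 0.5/0.855 = 0.58 with f = 0.5, and 0.5/0.822 = 0.61 with f = 0.8.
- 5–15% of terminations and 10–30% of spontaneous abortions after 14 weeks, counting only the four listed outcomes. Per 100 pregnancies, those reaching 14+0 number 62 + 1.4 + 1.1 + 0.9 = 65.4 up to 62 + 1.4 + 3.3 + 2.7 = 69.4. Termination risk is 0.9/65.4 = 1.4% to 2.7/69.4 = 3.9%. Against 18% the RR is 0.08–0.22. The four rates sum to only 92.4, so on a consistent base B2's risk is 18/92.4 = 19.5% and the RR is 0.07–0.20.

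**Late complications, third-trimester exposure.** If all cases arise in pregnancies that reach 28+0, null RR = 1/(1 − L). L = 0.10 gives 1.11; L = 0.29 (11% + 18%) gives 1.41.

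**Live birth and stillbirth, only if all pregnancies are the denominator.** On the 92.4 base, B2 live birth is 62/92.4 = 67.1%.
- Live birth, second trimester: 62/69.4 = 89.3% to 62/65.4 = 94.8%, RR 1.33–1.41.
- Live birth, third trimester, with half to all stillbirths after 28+0: 62/63.4 = 97.8% to 62/62.7 = 98.9%, RR 1.46–1.47.
- Stillbirth, third trimester, with 30–50% of stillbirths before 28+0 and L = 0.10–0.29: RR from 0.5/0.9 = 0.56 to 0.7/0.71 = 0.99.

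**Outcomes per birth.** For preterm birth (11%), if a share h of preterm births precedes the window, null RR = (1 − h)/(1 − 0.11h). This is 0.97 at h = 0.03 and 0.91 at h = 0.10.

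**The case against.** The strongest reply is that the mismatch is inferred. A reader might take the protocol to say that every B2 pregnancy, including those that ended early, enters each trimester comparison. It does not say so: section 5.7.4.3 does not mention trimester strata, section 5.7.4.2 gives denominators for cohorts, and the risk set of a conditional subgroup can be left to the SAP. That stands as a limit on the claim. It does not remove the point, because the protocol itself fixes strata, comparators and denominators, and an SAP that followed them literally would reproduce the mismatch.

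A reader might also infer that QUVIVIQ would look protective throughout. The documents do not support that. Late complications move toward harm, outcomes per birth or live birth hardly move, and Appendix 4 already drops third-trimester exposure for spontaneous abortion. Live birth and stillbirth have no stated analysis denominator, so their figures are conditional; Table 4 footnote a concerns power only.

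B2 is also not observed from conception. Women enroll while pregnant (section 5.2.1.1), only preferably before 20 weeks (section 5.2), and losses before enrollment may go unreported (section 5.9.1.3). This lowers the effective f, g and L and shrinks every figure above. Section 5.2 does, however, ask for enrollment as soon as the pregnancy is known, and the better that succeeds the larger the bias.

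Table 6 has a sensitivity analysis of spontaneous abortion by gestational age at enrollment. It covers one outcome and does not align risk sets by exposure window. Against B1 the bias would be smaller if B1 were split by its own exposure trimester, which is not stated.

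**Conclusion.** The point holds for spontaneous abortion, elective and therapeutic termination and pregnancy complications in the second- and third-trimester analyses against B2 and B, and for live birth and stillbirth if they use the same denominator. With no drug effect, second-trimester termination RRs of about 0.07–0.22 (or about 0.6 if half occur after 14 weeks) and spontaneous abortion RRs of about 0.11–0.87 would be expected; third-trimester preeclampsia would show about 1.11–1.41. These sizes rest on assumed gestational timing and on a comparator followed from conception, so they are upper bounds on what late enrollment would leave. Bias in both directions means that no single caveat on interpretation would cover it.

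These are secondary analyses run only as sample size allows. The primary A versus B1 comparison conditions both cohorts on first-trimester exposure to their own medication (section 5.7.1.3) and is not affected. The change should be made, but the main result does not depend on it.

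**What to change.** In section 5.7.2.1 and Appendix 4, state one of the following and carry it into the SAP.

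- **Preferred:** exposure is time-varying on the gestational-age scale, with delayed entry at enrollment in both cohorts, so that a woman counts as exposed only from her first exposure in the window.
- **Simpler:** for each trimester-specific comparison, women in Cohort A and in the comparator are both limited to pregnancies enrolled and ongoing at the same gestational age, and only later outcomes count in either.

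The enrollment condition must apply to both cohorts; set on the comparator alone, it would create a new imbalance. A landmark at the start of the trimester still leaves immortal time for a woman first exposed late in it (for example at week 26), which is why the time-varying form is better.

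With aligned risk sets the null RR is 1.00 by construction. Treatment start and stop dates and gestational age are already collected (section 5.6.1, Appendix 1). The cost is slightly more programming and fewer women and events. If half of terminations precede 14 weeks, 194 × 0.855 = 166 (f = 0.5) or 194 × 0.822 = 159 (f = 0.8) of the 194 B2 women would be ongoing at 14+0; under the landmark form, those enrolled later would also drop out.
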